## **11.5.7 Overdose**

In the event of an accidental or intentional overdose with the study drug (generally, an overdose is defined as at least twice the maximum daily dose per protocol), even if the seriousness criterion is not met, the Overdose Reporting Form should be completed and reported to the sponsor immediately (i.e., within 24 hours).

## 12 CLINICAL MONITORING

## 12.1 Investigator Responsibilities

The investigator undertakes to conduct this clinical trial in accordance with this study protocol, Good Clinical Practice (GCP) and applicable laws and regulations.

The investigator was required to ensure that the various procedures required by the clinical trial protocol and the various study procedures proposed by the sponsor, including safety regulations, were followed. The investigator agrees to provide reliable data and various information required by the clinical trial protocol in an accurate and legal manner in accordance with the instructions provided, and to ensure the sponsor's representative has direct access to/access to source documents.

The investigator may authorize other medical personnel he/she trusts to act as appropriate sub-investigators to assist in the conduct of the clinical study according to the requirements of the clinical protocol. All sub-investigators will conduct the study under the supervision of the investigator. The investigator will provide them with a copy of the clinical trial protocol and all necessary information.

#### 12.2 Sponsor Responsibilities

The sponsor of this clinical trial shall be responsible for the national regulatory authorities, and take all reasonable measures to ensure the moral ethics and compliance of the clinical trial as well as the authenticity and integrity of the case report form data records. Therefore, the main responsibility of the monitor is to assist the investigator and the sponsor to maintain a high level of moral, scientific, technical and regulatory quality in all aspects of the clinical trial.

During the course of the clinical trial, the monitor will periodically contact the trial site by visit, mail or telephone to review the progress of the study, the compliance of the investigator and patients with the clinical trial protocol and various urgent problems. During these monitoring visits, the monitor will review with the investigator the following details: patient informed consent forms, patient enrollment and follow-up, patient compliance with the study drug regimen, study drug assignment, study drug accountability, use of concomitant medications and other therapies, and data quality, SAE recording and reporting, and data quality.

1	1	Q	5

#### 13 DATA MANAGEMENT

## 13.1 Requirements for original documents

In accordance with ICH GCP guidelines, monitors must verify the eCRF against source documents unless it is pre-specified that source information is to be recorded directly on the electronic case report form (eCRF). The authorized person of the sponsor, the Ethics Committee and regulatory authorities can directly view the original documents of the data recorded in the eCRF (such as the patient's medical file, appointment book, original laboratory test results, etc.). These persons, subject to the principle of occupational confidentiality, must keep the identity or medical information of all subjects confidential.

## 13.2 Case Report Forms and Precautions

The EDC system was used in this study to process clinical trial data. The case report forms (CRFs) for this study will be in electronic data format, depending on the method of data collection.

Each subject had a separate, complete eCRF form. All completed original eCRF forms are the sole property of Shanghai Miracogen Inc. Unless authorized by Shanghai Miracogen Inc. or relevant government authority, any third party cannot obtain and use the data in eCRF.

It is the responsibility of the investigator to complete all trial data required by this protocol on the eCRF forms. The investigator is also obliged to ensure that the data in the eCRF form are consistent with those in the original medical records. The eCRF is a controlled document. The investigator must sign the eCRF and ensure the authenticity, accuracy and integrity of the data. If modification is required, the modification record information will be automatically recorded in the EDC system.

The clinical research associate (CRA) should ensure the authenticity, accuracy and completeness of the data by verifying the original medical records, checking the completed eCRF and other study-related information during each monitoring visit.

#### 13.3 Application of Computer System

A computerized system will be used to generate, modify, maintain, archive, and restore all data collected in the clinical study.

#### 13.4 Data collection

This study will collect clinical study data using the EDC system. Case form forms (CRFs) for this study will be in electronic data format.

## 13.5 Data Management and Quality Control

The data administrator shall, together with the principal investigator, propose the contents of data range check and logic check according to the range and interrelation of each indicator value in the case report form. Compile the corresponding computer program, control the input of wrong data before input, find out the cause of error and make correction. All the error contents and modification results shall be recorded and properly preserved.

Data verification will be divided into manual verification and system verification. Manual verification is medical verification, which checks the consistency and logic of data from the perspective of medical specialty. System verification is to verify the database by writing SAS program and automatically sort out the data that does not meet the requirements of clinical study by running the system program. For any question in the eCRF, DM will generate a question in EDC. The investigator should answer the question in EDC system as soon as possible and possibly modify the data. DM will confirm whether to close the question based on the investigator's answer and the updated data, and can raise the question again if necessary, until all the questions are resolved. All modifications and updates will be documented and archived.

CDISC standards were implemented for data management in this study.

#### 13.6 Data Retention

In the face of inspections and audits by government regulatory authorities and Shanghai Miracogen Inc., the investigator agrees to retain all original documents, photocopies, meeting minutes and physical objects related to the subjects in this study. It is recommended that the investigator retain the study file for at least 15 years after the trial is completed or halfway stopped. If the Investigator is no longer able to retain the study documentation, the Sponsor must be notified and the relevant documentation transferred to a third party acceptable to both parties. Within 15 years after the end or discontinuation of the clinical trial, the investigator must obtain a written letter of authorization from the sponsor before disposing or destroying the study data and archives.

#### 13.7 Modification to Test Protocol

The investigator should not deviate from the current clinical trial protocol without sponsor approval and prior approval/favorable opinion or filing of the amendments by the Clinical Institutional Review Board and Ethics Committee, unless the changes eliminate an immediate hazard to study subjects or the changes involve only logistical or administrative aspects of the trial. Any amendment agreed should be documented and the written amendment should be signed by both the investigator and the sponsor, and archived together with the clinical trial protocol.

In some cases, it may be necessary to modify the informed consent form at the same time. The investigator must approve/acknowledge the written ICF amendment by IRB and EC before implementing the amendment.

## 13.8 Principles for publication and sharing of trial results

The investigator has the right to use the results obtained from the clinical trial for teaching and communication in meetings and publications. In order to ensure the accuracy and scientificity of information, while protecting the independence and responsibility of investigators and protecting the confidentiality of information, only verified and valid materials can be used. For this reason, any publication or communication, or draft publication or communication by the Investigator shall be preceded by communication and discussion among all parties. Therefore, the investigator undertakes and ensures that all sub-investigators undertake not to make any publication, communication or release of the results of the study without the written consent of the sponsor.

The investigator must provide the sponsor with a copy of the manuscript for review at least 45 days prior to journal submission or 20 days prior to abstract submission. Publication must be postponed for no more than 90 days before a written response is received from the sponsor, which is understood to mean that the sponsor cannot refuse publication without proper reason. The investigator agrees to the modifications requested by the sponsor, which should not jeopardize the accuracy or scientificity of the publication.

In a multi-center study, the investigator agrees not to publish the relevant results of his/her study site before the overall study results are published. If no results are published within 12 months after the termination of the clinical trial in all the study sites, the investigator has the right to independently publish the results of the clinical trial in this study site, and the review procedure is described as before. If the clinical trial is managed by a steering committee, the latter may develop detailed provisions for publication.

The investigator should not use the name of the sponsor and/or its employees in advertising or promotional materials or publications without the written consent of the sponsor. The Sponsor shall not use the names of the Investigator and/or his/her colleagues in advertising or promotional materials or publications without the written consent of the Subject or Investigator.

The sponsor has the right to publish the study results at any time.

## 14 STATISTICAL ANALYSIS

#### 14.1 Sample Size

The number of patients with advanced solid tumors in Phase Ia needs to be determined based on the results of patient safety evaluation in the actual dose escalation trial. The expected number of patients is approximately 26.

A total of 36 patients (12 in each category) with advanced colorectal cancer, head and neck squamous cell carcinoma, and nasopharyngeal carcinoma were evaluable for the phase Ib trial. Since this study is an exploratory Phase I clinical trial, the number of patients participating (i.e., sample size) is not based on formal statistical calculations.

#### 14.2 Statistical Analysis Plan

Statistical analysis was performed using SAS Enterprise version 5.1 (or higher) software. The study results will be summarized and analyzed by descriptive statistical methods for safety indicators and efficacy indicators.

Kinetic parameters include but are not limited to  $C_{max}$ ,  $T_{max}$ ,  $t_{1/2}$ , MRT,  $V_d$ , CL, AUC0-t and AUC0-inf, etc.; kinetic analysis is performed according to non-compartmental model; concentration and kinetic parameter pharmacokinetic analysis software is used for evaluation.

The analytical parameters of immunogenicity include ADA positive rate and antibody.

The detailed statistical analysis strategy and steps will be described in a separate Statistical Analysis Plan (SAP). After the start of the trial, for the modification of primary study objectives and important secondary study objectives, or changes in corresponding statistical analysis methods, the protocol and statistical analysis plan need to be amended and the final version should be obtained before database lock. After database lock, additional exploratory analyses not included in the protocol or statistical analysis plan will be described in detail in the clinical trial report (CSR).

#### 14.3 Data Analysis Set

Safety Set (SS): includes all subjects who received at least one treatment. Safety analysis set is used for safety analysis and primary analysis of efficacy indicators.

Evaluable Analysis Set: Phase Ia includes subjects who have at least one post-treatment tumor assessment; Phase Ib includes subjects who have not achieved CR and PR response and have at least one evaluable baseline post-treatment tumor assessment, and subjects who have achieved CR and PR response include at least two post-treatment tumor assessments (and are at least 4 weeks apart). The evaluable analysis set was used for secondary analyses of efficacy measures.

PK Analysis Set (PKS): includes subjects who received at least one treatment and had at least one valid post-treatment PK concentration measurement. The PK analysis set was used for the analysis of PK parameters.

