In the first-in-human (FIH) study at MTD/RP2D, according to the comprehensive evaluation on the first-in-human (Saber-2015) dose of ADC by US FDA, it is considered that one-sixth of the highest non-severely toxic dose (HNSTD) calculated by body surface area in cynomolgus monkeys is selected as the first-in-human (FIH) dose, which is an acceptable initial dose for phase I clinical study under the condition of balanced safety and efficacy. Therefore, it can be speculated that 0.3 mg/kg MRG003 can be used as the initial dose in human clinical trials. However, with reference to the U.S. FDA Guideline on Estimating the Maximum Safe Starting Dose for Initial In-Human Clinical Trials, the calculated starting dose of MRG003 in human clinical trials is 0.2 mg/kg, and for safer consideration, the starting dose of MRG003 is preliminarily set as 0.1 mg/kg. A total of 8 dose levels (0.1, 0.3, 0.6, 1.0, 1.5, 2.0, 2.5, 3.0 mg/kg) were designed. If no MTD is

observed in these dose groups, dose escalation will continue in a 3 + 3 manner by escalating no more than 20% of the previous dose level until the MTD is reached.

In the phase Ia study, the concentrations of three components of MRG003 in the systemic circulation of subjects, total antibody, conjugated antibody and unconjugated drug, will be detected, and the PK parameters of the above three components will be analyzed. In addition, it is also necessary to detect anti-drug antibody.

In Phase Ib, a total of 36 eligible subjects with advanced colorectal cancer, head and neck squamous cell carcinoma and nasopharyngeal carcinoma were treated with intravenous drip of MRG003 at MTD/RP2D for 8 cycles in the same dosing regimen as in Phase Ia. To assess the objective response rate (ORR = CR + PR), stable disease (SD), progressive disease (PD), progression-free survival (PFS), overall survival (OS) and duration of response (DOR) of MRG003 on tumors during the treatment and follow-up periods, and to assess the safety, tolerability and kinetics of MRG003.

Phase I clinical study will provide the final MTD/RP2D dose and PK data and preliminary results of the efficacy and safety of the study drug for phase II clinical trial.

The Safety Monitoring Committee (SMC) is responsible for safety supervision, dose escalation design, MTD or RP2D, and other important study decisions. However, in case of disagreement between the trial sponsor and the SMC, the decision process will be described in the SMC Charter.

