# **6.5 Efficacy Assessments**

Response to tumor therapy will be assessed in this study using Response Evaluation Criteria in Solid Tumors RECIST v1.1, see Appendix II.

The primary outcome measure of Ib trial is objective response rate (ORR), the proportion of subjects with confirmed overall CR and confirmed overall PR in all subjects who have received the study drug.

Progression-free survival (PFS) for this study is defined as the time from the start of treatment with MRG003 until objective tumor progression or death from any cause. Duration of response (DOR) is defined as the time from the first documented response until disease progression or death among subjects with a confirmed objective response (CR or PR), with tumor evaluation according to RECIST v1.1 criteria. Overall survival (OS) is defined as the time from the start of treatment with MRG003 to death due to any cause.

For patients without disease progression after the last dosing cycle, tumor response should be assessed every 6 weeks and followed up for survival until disease progression or other anti-tumor treatment. Survival follow-up could be performed every 12 weeks after confirmation of disease progression or receipt of additional antineoplastic therapy. The follow-up period starts from the end of treatment cycle until death or study termination. During follow-up, survival status and subsequent tumor treatment need to be examined and recorded. Subsequent tumor treatment does not need to be recorded in electronic case report form (eCRF).

Tumor evaluation will be performed according to RECIST v1.1, and the results of imaging assessment methods should be recorded in the electronic case report form. During trial treatment, radiographic assessments may be performed  $\pm$  7 days from the scheduled date and the methodology should be consistent between baseline and subsequent follow-up. Whenever clinically permissible, the same oral or intravenous contrast agent was used for each scan, and, whenever possible, the same investigator/radiologist evaluated all patient scans during the study.

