#### 14.4.4.2 Secondary Outcome Measures in Phase Ib

- Drug safety and tolerability will be assessed. Descriptive statistical methods will be used to analyze and summarize the types and severity of adverse events and their correlation with the study drug.
- At MTD/RP2D, within the treatment cycle of intravenous drip of MRG003, determine the concentrations of the three drug components in all subjects, and calculate the drug PK values, not limited to Cmax, Tmax, t1/2, MRT, Vd, CL, AUC0-t and AUC0-inf; perform kinetic analysis according to non-compartment model; evaluate the concentration and pharmacokinetic parameter pharmacokinetic analysis software.
  - Anti-therapeutic drug antibody (ADA) analysis: Descriptive statistical analysis was performed using the percentage of ADA positive, and the range of each ADA positive subject was listed.
- To assess the best response of subjects throughout the trial according to RECIST v1.1 criteria: complete response (CR), partial response (PR), stable disease (SD), progressive disease (PD) and non-evaluable (NE). The number and proportion of subjects in each efficacy endpoint will be summarized and described. The best response in Phase Ib requires confirmation by two assessments.

• To assess tumor efficacy measures in relation to time: progression-free survival (PFS), overall survival (OS), and duration of response (DOR). The product limit method was used to calculate the estimated survival time and 95% confidence interval, and the survival time and its confidence interval in the first and third quartiles (Q1, Q3). Survival curves were plotted with the Kaplan-Meier method.

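### Protocol section 14.3 makes entry to the Phase Ib evaluable set depend on response, so a subject whose only post-treatment scan shows CR or PR can drop out of the secondary ORR denominator

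*Protocol*

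**What the plan says.** Protocol section 14.3 defines the evaluable set in two ways. For Phase Ia, one post-treatment tumour assessment is enough, whatever it shows. For Phase Ib the rule splits by result. The first branch reads "Phase Ib includes subjects who have not achieved CR and PR response and have at least one evaluable baseline post-treatment tumor assessment". The second reads "subjects who have achieved CR and PR response include at least two post-treatment tumor assessments (and are at least 4 weeks apart".

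The same section fixes what each set is for. On the Safety Set, which is everyone treated at least once: "Safety analysis set is used for safety analysis and primary analysis of efficacy indicators". On the other set: "The evaluable analysis set was used for secondary analyses of efficacy measures".

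Two other places say what counts as a response in Phase Ib. Section 6.5 defines the primary ORR as "the proportion of subjects with confirmed overall CR and confirmed overall PR in all subjects who have received the study drug". Section 14.4.4.2 adds: "The best response in Phase Ib requires confirmation by two assessments". Section 14.4.3.2 divides CR plus PR by the number of subjects in the analysis set, so the definition of the set fixes the denominator.

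On size, section 14.1 has "A total of 36 patients (12 in each category" and calls them evaluable, as do section 7.1 and the subject-population entry of the synopsis. Section 6.1 has "a total of 36 eligible subjects with advanced colorectal cancer", and the design text of the synopsis uses the same term.

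**The concern.** Membership of an analysis set should not depend on the result that the set is used to estimate. Here it does. Take two subjects who each have one post-treatment scan and then leave. The one with SD or PD stays in the Phase Ib evaluable set. The one with PR does not. Neither has a confirmed response, so both are non-responders under sections 6.5 and 14.4.4.2, yet only one is counted.

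The situation can arise in practice. Scans are six weeks apart and confirmation comes six weeks after the first CR or PR (Table 6, note q; section 9.6). In that interval a subject can die, withdraw or be lost to follow-up (sections 7.5 and 9.8).

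At stake is the secondary ORR by tumour type. With 12 subjects per type, losing one from the denominator moves the estimate visibly, and always in the favourable direction.

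**Working it through.** **The plan's own figure.** The Phase Ib size is 3 tumour types × 12 = 36, which agrees with section 14.1. The protocol states that this size does not come from a formal calculation, and it gives no ORR, alpha or power to reproduce.

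**Who is dropped.** The second branch asks for two post-treatment assessments at least 4 weeks apart. It does not ask that the second confirm the first. Scheduled scans are 6 weeks apart, and section 6.5 allows ± 7 days on each, so two consecutive scheduled scans are at least 42 − 7 − 7 = 28 days apart, which is 4 weeks. Hence:

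- PR at week 6, not confirmed at week 12: two scans, stays in as a non-responder.
- SD at week 6, PR at week 12, no later scan: two scans, stays in as a non-responder.
- CR or PR at the only post-treatment scan: one scan, dropped.
- SD or PD at the only post-treatment scan: one scan, stays in.

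On the planned schedule the affected group is therefore essentially subjects with a single post-treatment scan that shows CR or PR.

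**Formulas.** Let N be the number treated, x the confirmed responders, u the subjects dropped as above, and m the subjects with no post-treatment scan.

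- Safety Set (primary): x / N
- Evaluable set as written: x / (N − u − m)
- Evaluable set with one entry rule for all: x / (N − m)

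For x > 0 and u > 0 the second always exceeds the third. The values of x, u and m below are assumptions, because the protocol gives none. Intervals are exact (Clopper-Pearson), also an assumption, since the protocol asks for a 95% CI without naming a method.

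**One tumour type, N = 12, x = 3, m = 0.** The Safety Set and the single-rule set both give 3/12 = 25.0% (5.5 to 57.2).

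| u | As written | 95% CI (%) | Shift (points) |
|---|---|---|---|
| 0 | 3/12 = 25.0% | 5.5 to 57.2 | 0 |
| 1 | 3/11 = 27.3% | 6.0 to 61.0 | +2.3 |
| 2 | 3/10 = 30.0% | 6.7 to 65.2 | +5.0 |
| 3 | 3/9 = 33.3% | 7.5 to 70.1 | +8.3 |

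**Other response counts, N = 12, m = 0.** For u = 1, 2, 3 the shift is +1.5, +3.3, +5.6 points with x = 2, and +3.0, +6.7, +11.1 points with x = 4.

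**All three types pooled, N = 36, x = 9, m = 0.** The base is 9/36 = 25.0%. As written: 9/34 = 26.5% (u = 2), 9/32 = 28.1% (u = 4), 9/30 = 30.0% (u = 6).

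**Separating the two causes of a smaller denominator.** With N = 12, x = 3, u = 1, m = 1: Safety Set 3/12 = 25.0%, single-rule set 3/11 = 27.3%, as written 3/10 = 30.0%. Of the 5.0-point gap, 2.3 points come from the subject with no scan, whom any one-scan rule would also leave out. Only 2.7 points come from the rule in question.

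**The case against.** The strongest reply is that *achieved* in section 14.3 means achieved with confirmation. A subject with an unconfirmed PR has then not achieved a response, enters under the one-scan branch and stays in the denominator. The bias disappears. This reading fits sections 6.5 and 14.4.4.2. Against it, section 14.3 does not say confirmed, and on this reading the two-scan condition is nearly redundant, since a confirmed responder already has two assessments. The reply shows that the wording is ambiguous. It does not show that the wording is safe.

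A second reply is that few subjects can be affected. Section 9.7 continues six-weekly imaging after treatment in subjects without progression, and section 9.8 asks for imaging to continue after a stop for an adverse event. Both narrow the group, but neither helps with death, withdrawal of consent or loss to follow-up. This reply stands as to likely size.

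Three stronger conclusions are tempting, and the protocol does not support them:

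- *That the Phase Ib ORR as such is inflated.* The primary ORR is taken over all treated subjects, so a single-scan PR stays in that denominator as a non-response.
- *That all unconfirmed responders disappear.* Those with a second scan at least 4 weeks apart stay in.
- *That subjects are replaced because of their outcome, so that the number treated depends on response.* No Phase Ib replacement rule exists; the one in section 6.3.4.1 concerns DLT evaluability in Phase Ia. Nothing in the text equates the 36 evaluable patients with the set defined in section 14.3.

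**Conclusion.** The point holds in a limited form. Read literally, section 14.3 lets the result decide who enters the Phase Ib evaluable set, contrary to the protocol's own confirmed-response rule, and this can only push the secondary ORR upward. In a cohort of 12 with 3 confirmed responders the shift is 2.3 points for one affected subject and 5.0 for two, and zero if there is none. These counts are assumed, and the intervals at this size are far wider than the shift. The primary ORR does not change. The analysis concerned is secondary and descriptive, so the matter is minor to moderate, but the direction of the error is known in advance and it is easily removed.

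The use of both *evaluable* and *eligible* for the 36 subjects is a real inconsistency of terms. It leaves open whether 36 counts treated subjects or members of the section 14.3 set. It is not evidence of outcome-driven enrolment.

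**What to change.** In section 14.3, replace the two Phase Ib branches with one rule of the Phase Ia kind: subjects who were treated and have at least one evaluable post-baseline tumour assessment, whatever it shows. Add that a CR or PR without confirmation counts as non-response and remains in the denominator.

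Use one term for the 36 Phase Ib subjects in the synopsis and sections 6.1, 7.1 and 14.1, and state whether it means subjects treated or members of the section 14.3 set.

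The cost is a few sentences, with no new data, visits or assessments. The secondary ORR may come out slightly lower than under the present wording.
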